12.2 Screen Fail Criteria

Any consented participant who is excluded from the study before enrollment is considered a screen failure. All screen failures must be documented with the reason for the screen failure adequately stated. If a participant screen fails prior to enrollment, they can be rescreened up to 3 times if the site staff feels they meet eligibility criteria. Rescreened participants will have to complete all screening procedures (i.e., data from previous screenings cannot be used). Lab test screening may be done twice per screening.

12.3 Early Withdrawal of Participants from the Study

All participants are free to withdraw from participation at any time, for any reason, specified or unspecified, and without prejudice. This may include participants who withdraw from study treatment early and who decline to continue to come in for remaining follow-up visits or it may include participants who completed treatment and decline to come in for remaining follow up visits.

Reasonable attempts will be made by the investigator to provide a reason for early participant withdrawals. The reason for the participant's early withdrawal from the study will be specified in the participant's source documents. Participants who withdraw early from the study should be encouraged to come in for a final early study withdrawal visit (and the procedures to be followed would include those for their next scheduled visit).

12.4 Replacement of Participants

Participants who withdraw from the study after having been both enrolled and having received at least 1 dose of ABI-009 will not be replaced. Participants may be replaced if they have been enrolled but withdraw prior to receiving any study drug or fail minimum seizure frequency required to receive study drug (≥ 8 seizures over the past 30 days with ≤ 2 weeks without seizures).

13 PROTOCOL VIOLATIONS

A protocol violation occurs when the participant, investigator, study staff or the Sponsor fails to adhere to the protocol requirements. Protocol violations for this study include, but are not limited to, the following:

- Failure to meet inclusion/exclusion criteria
- Inappropriate administration of study drug
- Failure of adherence to study schedule

Failure to comply with Good Clinical Practice (GCP) guidelines will also result in a protocol violation. The principle investigator will determine if a protocol violation should result in early permanent discontinuation of ABI-009 dosing for a participant.

When a protocol violation occurs, it will be discussed with the investigator and a Protocol Violation Form detailing the violation will be generated. This form will be signed by the Investigator. A copy of the form will be filed in the site's regulatory binder. The site will report the violation to their IRB in accordance with their IRB reporting requirements.

14 DATA SAFETY MONITORING

An independent Data Safety Monitoring Board consisting of at least three members will convene as frequently as necessary to review all participants enrolled on study. The DSMB will convene at minimum before the opening of each dose escalation cohort, and before opening MTD cohort expansion. All AEs experienced by participants on study will be summarized for review by the DSMB regardless of suspected relationship to the study drug. SAEs which are determined to be possibly, probably or definitely related to study drug will be reported to the DSMB within 5 days of occurrence, and any death of a participant that occurs while they are actively on study, regardless of relatedness to study drug, will be reviewed by the DSMB prior to enrollment of subsequent participants on study.

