STUDY DESIGN	This is a prospective, single-center, phase 1 safety study to investigate the safety, tolerability, seizure control, and quality of life in participants with medically-refractory epilepsy who failed epilepsy surgery. These participants will have continued seizures despite being at least 3 months post-epilepsy surgery (resective surgery with an intent to cure). Upon enrollment, participants will be continued and observed on their pre-existing, clinically prescribed antiepileptic drug (AED) regimen for 1 month. At the 1-month mark, participants will receive weekly ABI-009 intravenously at different dose levels in cohorts of 3 participants each using the standard 3+3 dose-finding design. ABI-009 will be continued for a total of 3 weeks. ABI-009 will then be discontinued and the participants will be observed for an additional 3 months. We intend an expansion of the maximum tolerated dose (MTD) cohort to an estimated additional 6 participants for a maximum possible enrollment of 18 participants.
DURATION OF SUBJECT PARTICIPATION	Participants will be on study for about five months. Initial control period: 1 month Dosing period: 3 weeks

AND DURATION OF STUDY	Follow-up: 3 months
PRIMARY OBJECTIVE	
Safety and Tolerability:
 
 ▪ Determine dose-limiting toxicities (DLTs) and MTD of ABI-009 in participants with surgically-refractory epilepsy ▪ Record the adverse events (AEs) and document their severity with ABI-009 dosing for medically intractable epilepsy that has failed surgical resection, administered in conjunction with their pre-existing AED regimen. Record the compliance of families with medication and record the number of participants that withdraw from study either voluntarily or by necessity secondary to AEs. ▪ Columbia-Suicide Severity Rating Scale (C-SSRS) serious suicidal ideation score stays below a 4 rating.

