Dose-levels	ABI-009 in mg/m ²												
-2	1												
-1	2.5												
1	5												
2	10												
3	20												

	
then a new cohort of 3 participants at the next higher dose level can be enrolled. If 2/6 participants at dose level 1 experience a DLT, then that cohort will be closed to further enrollment and 3 participants will be enrolled at the next lower dose level, and so on. The MTD is the highest dose level in which ≤ 1 participant has a DLT.
 
Once the MTD has been determined, the MTD cohort will be opened for an additional 6 participants. These participants will adhere to the identical protocol of the rest of their cohort.
 
Product will be administered IV every seven days for three weeks.

CONTROL PRODUCT, DOSE AND ROUTE OF ADMINISTRATION	
There is no control product for this study. Participants will serve as their own controls by continuing their pre-existing AED regimen for 1 month after enrollment prior to starting dosing with ABI-009. In order to proceed with drug administration participants will have to have had >8 seizures in 30 days without 2 consecutive weeks of seizure freedom.

CONCOMITANT MEDICATIONS	
Allowed: Standard therapy for epilepsy is allowed except for treatments noted in the prohibited medications section below. Pre-existing AEDs must not be titrated while participants are enrolled in the study, unless the dose change is solely to address subtherapeutic levels as determined by the treating neurologist. Rescue medication is allowed for prolonged seizure event or cluster of seizures.
 
Prohibited: The following medication changes are prohibited during participation in the trial, and as such will be considered a protocol violation:
 
 • Any changes in dosage of AED regimen, unless solely to address subtherapeutic levels of AEDs as determined by the treating neurologist. • Any additions or removal of AEDs to the participant's AED regimen during participation unless medically necessary and discussed with investigator
PRIMARY ENDPOINT	
Safety:
 
DLT and MTD
 
Incidence of adverse events and clinically significant abnormal lab values
 
Tolerability:
 
Number of participants withdrawn from study
 
Adherence to prescribed ABI-009 regimen
 
Columbia-Suicide Severity Rating Scale (C-SSRS) serious suicidal ideation score stays below a 4 rating.

SECONDARY	
Efficacy:

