6 PARTICIPANT SELECTION

6.1 Study Population

Participants with a diagnosis of medically intractable epilepsy who meet all of the inclusion and none of the exclusion criteria will be eligible for participation in this study. Participants must be enrolled before study procedures begin.

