7.1 Allowed Medications and Treatments

Standard therapy for epilepsy and related conditions is allowed except for treatments noted in the exclusion criteria described above and as noted in the prohibited medications section below. A stable therapeutic regimen between screening and Visit 1 is the goal, as well as through the baseline period. Once enrolled and started into the baseline observation period, changes in AED medication regimen are not permitted unless it is solely for dose adjustments secondary to sub- or super-therapeutic serum levels. Participants that have been on a chronic AED regimen will be mandated to continue them throughout the entire study period. Treatment for prolonged seizures (>5 minutes) or clusters of seizures can be used per participant's previous rescue prescription.

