10.3 Visit 2 – End of Baseline (Day 30 +5/-2 days)

1. Review participant diary for compliance and seizure frequency.
2. Ensure participant has had >8 seizures in the last 30 days without 2 weeks of seizure freedom to continue onto next phase.
3. Collect baseline AEs
4. Administer C-SSRS, QOLCE and NCBRF
5. Record changes to concomitant medications.
6. Perform abbreviated physical exam
7. Obtain and record vital signs. Pulse oximetry must be >93 to continue.
8. Collect blood for clinical laboratory tests (chemistry, hematology).
9. Collect urine for pregnancy test (if child-bearing potential).
 - a. If positive confirm with blood test
10. Laboratory assessments as required per the schedule of evaluations
 - a. Complete Blood Count (CBC) with differential and platelet count.
 - b. Blood chemistry assessment, including:

- i. Sodium, potassium, chloride, bicarbonate, calcium, fasting glucose, albumin,
- ii. Total protein, BUN, serum creatinine.
- iii. Total bilirubin, AST, ALT, alkaline phosphatase, uric acid, phosphorus,
- iv. Fasting serum lipid profile (total cholesterol, triglycerides, HDL and LDL)

11. Coagulation assessment, including prothrombin time, partial thromboplastin time, international normalized ratio (PT/PTT/INR).

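### After an on-study death, section 14 ties DSMB review to further enrollment only, so participants already enrolled can be infused before that review

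*Combined protocol and SAP*

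**What the plan says.** Section 14 requires that any death of a participant on study, whatever its cause, "will be reviewed by the DSMB prior to enrollment of subsequent participants on study". The same section asks the board to meet as often as it needs to, and at least before each escalation cohort and before the expansion. It also requires SAEs judged at least possibly related to study drug to reach the board within 5 days of occurrence.

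Enrollment is not the start of exposure in this trial. The synopsis (Study Design) states: "Upon enrollment, participants will be continued and observed on their pre-existing, clinically prescribed antiepileptic drug (AED) regimen for 1 month". The synopsis entry on the control product has participants continue their AEDs "for 1 month after enrollment prior to starting dosing with ABI-009". Section 7.1 treats enrollment as the entry to baseline: "Once enrolled and started into the baseline observation period, changes in AED medication regimen are not permitted". Section 12.4 recognises participants who are enrolled but undosed: "Participants may be replaced if they have been enrolled but withdraw prior to receiving any study drug". The gate to dosing is at Visit 2 (section 10.3) and concerns seizure counts: "Ensure participant has had >8 seizures in the last 30 days without 2 weeks of seizure freedom to continue onto next phase".

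**The concern.** A rule requiring independent review after a death should protect the people nearest to the next exposure. Here it acts on those furthest from it. A person not yet enrolled is about a month from Dose 1, whereas someone at the end of baseline or between infusions may be days or hours away. The rule stops the first and says nothing about the second.

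At stake is whether a child can receive a first or further infusion of an immunosuppressive study drug after another participant has died and before the independent board has considered why. Section 2.1 notes that drugs of this class have occasionally caused fatal infections and, rarely, fatal pneumonitis. Section 1.13 states that no pediatric PK data exist for ABI-009. Section 14 already declines to leave the response to a death to local judgment alone, but it attaches the requirement to the wrong event.

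**Working it through.** The plan gives no figure of its own on this point. The check is timeline arithmetic, a search of the text for a hold, and a rough event rate.

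1. **Enrollment to Dose 1.** Inputs: Visit 2 is at Day 30, +5/−2 days (10.3); Visit 2 may also be Dose 1 (Appendix 1 footnote); enrollment is taken as Day 0. Earliest 30 − 2 = Day 28; latest 30 + 5 = Day 35. If Visits 2 and 3 are separate, the lag is longer, but no interval is stated.

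2. **End of dosing.** Infusions are 5–9 days apart (8.4.1), so two intervals take 10–18 days. The third infusion falls between Day 28 + 10 = 38 and Day 35 + 18 = 53. A participant enrolled the day before a death could complete the course by then without section 14 requiring the review first.

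3. **Infusions outside the rule, per participant.** In baseline, 3; after Dose 1, 3 − 1 = 2; after Dose 2, 3 − 2 = 1. The documents do not say how many participants would be in these states at once. As an illustration, if a death occurs in a cohort of 3 while both others are undosed, 2 × 3 = 6 infusions are uncovered. In the 6-participant expansion with the other five undosed, the figure is 5 × 3 = 15.

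4. **Search for a hold elsewhere.**
   - 8.6 interrupts dosing for the participant's own toxicity.
   - 10.4 lists dose modification for such toxicities and has no step concerning events in other participants.
   - 11.2.1 sends SAE reports, related or not, to the site investigator, study chair and drug supplier within one business day of the site learning of the event. It does not mention infusions.
   - 12.1 permits permanent discontinuation of an individual at any time.
   - 17.1 and 17.5 allow departures from the protocol to protect participants.

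   Each gives notice or permission. None requires an infusion to wait.

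5. **The 5-day report.** Section 11.1 has five attribution categories. The 5-day duty covers three of them (possible, probable, definite) and leaves out unlikely and unrelated. Because infusions may be 5 days apart, the next one can be given before or on the day the report is due. The duty continues after the last enrollment, but it carries no deadline for the review itself.

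6. **How often this could arise.** Inputs: 18 participants, 0.5% deaths per year (2.1), and 5 months (synopsis) or 18 weeks (4.1) on study. Expected background deaths: 18 × 5/12 × 0.005 = 0.0375, or 18 × 18/52 × 0.005 = 0.0312. Chance of at least one: 1 − exp(−0.0375) = 3.7%, or 1 − exp(−0.0312) = 3.1%.

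**The case against.** The strongest reply is that the protocol already has several layers of protection. A possibly related death must reach the board within 5 days, and the board may meet whenever needed to review everyone enrolled. This is a single-site study run by a sponsor-investigator, so those notified can stop dosing themselves. Immediate hazards can be acted on without prior IRB approval. Section 10.4 does not forbid a safety hold, and section 8.6.3, on missed doses, states an intention to keep to the weekly schedule rather than an order to infuse. The site safety-monitoring plan (11.3) and the Study Continuation and Dosing Checklists (Appendix 1) are not reproduced and could contain a hold. A blanket hold would also stop infusions after the death of someone never dosed.

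Most of this stands, and it limits the point to the protocol text. It does not remove it: discretion and notice are not a required review, and checklists whose contents are not shown cannot be credited. The remark about an undosed participant's death is fair and is reflected in the fix.

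Three stronger readings are tempting and not supported:
- A reader might infer that dosing must go on after a death. The text permits it but does not require it.
- A reader might infer that the board would not be told, or that the site always knows within one business day. The 5-day duty answers the first. The one-business-day clock starts only when the site learns of the event, and nothing says how soon that is.
- Section 6.1 says "Participants must be enrolled before study procedures begin", so a reader might date enrollment to the start of screening (Day −14) and claim a lag of 35 + 14 = 49 days. Section 12.2 places screen failure before enrollment, and the synopsis starts the one-month observation at enrollment, so 28–35 days fits better.

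**Conclusion.** The point holds as a gap in section 14. Required DSMB review of a death precedes new enrollment only. One to three infusions per already enrolled participant fall outside it, and after the last enrollment there is no time limit.

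The practical size is small. The 3–4% is the chance of any background death across all participation, including drug-free baseline and late follow-up. It is not the chance that the gap matters, and it excludes any drug-related risk, for which the documents give no rate. The conclusion assumes enrollment at Day 0, Visit 2 doubling as Dose 1, and no hold in the unseen site documents. This is an inexpensive improvement to a safety rule; it does not show that participants would in fact be dosed before review.

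**What to change.** Reword the last part of section 14 along these lines:

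- Any on-study death is reviewed by the DSMB before further enrollment and before the first infusion of any participant not yet dosed.
- For participants between doses, the next infusion is held until the DSMB, or its chair by expedited review, clears it. This hold may be limited to deaths of dosed participants that have not yet been judged unrelated.
- The review is completed within a fixed time of the site learning of the death, for example 7 days (an assumed value), including after the last enrollment.
- Such holds are not protocol violations (section 13). They do not count toward the 3-week delay rule (8.6, 11.4) or against infusion compliance (15.4) or per-protocol status (15.1.1).
- If Dose 1 is delayed, state whether the Visit 2 seizure count stands or is repeated. The analysis baseline stays at Days 0–30 (15.1).

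The per-protocol protection matters because 2/3 = 67% falls below the >80% threshold. With three doses all must be given, and a major violation also excludes a participant.

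The cost is a few sentences, using the existing board. With a 7-day deadline, the longest gap between infusions is 9 + 7 = 16 days. That is 16 − 7 = 9 days past the nominal weekly day, below the 21-day limit. The downside is a rare, short delay that may fall outside a visit window, disturb the three weekly troughs, or require the seizure-count check to be repeated.

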15 STATISTICAL METHODS AND CONSIDERATIONS

15.1 General Considerations

Prior to the analysis of the final study data, a detailed Statistical Analysis Plan (SAP) will be written, describing all analyses that will be performed. The SAP will contain any modifications to the analysis plan described below.

For the purposes of analyses, baseline period will be defined as Days 0-30. Except where otherwise noted, comparisons of continuous variables between pre and post treatment periods will utilize t-tests or linear regression, test of proportions and analysis of count data using Poisson regression. Except where otherwise noted, all tests will be two-sided and statistical significance will be determined at the 0.05 level. Missing data methods for the primary and key secondary endpoints will be described in the SAP. No adjustment for multiple comparisons will be made.

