4 STUDY DESIGN

4.1 Study Overview

This is a prospective, single-center, non-randomized open-label phase 1 study to investigate multiple dose levels of ABI-009 for surgically-refractory epilepsy. Up to 18 participants are planned to be enrolled into the study.

The duration of participation for each participant is up to 18 weeks, including a 4-week baseline period to obtain baseline outcome rates, a 3-week active study period and a 12-week follow-up period (see Figure 1). After the baseline period, participants will be started on the assigned dose of ABI-009, given once weekly for a total of 3 weeks. Dose levels to be tested are below:

For dose finding, ABI-009 will be tested in cohorts of 3 participants each using the standard 3+3 dose-finding design. Initial starting dose will be at 5 mg/m²/week.

Table 3: ABI-009 Cohort Dosing Schedule

Dose levels	ABI-009 in mg/m ²
-2	1
-1	2.5
1	5
2	10

3	20
---	----

Escalation to the next dose level with a new cohort of 3 participants will occur after no DLT was observed. There will be no intra-participant dose escalation allowed. If a DLT occurs in a cohort, an additional 3 participants will be recruited to the cohort. If no further DLTs occur, then a new cohort of 3 participants at the next higher dose level can be enrolled. If 2/6 participants at a dose level experience a DLT, then the cohort will be closed to further enrollment and 3 participants will be enrolled at the next lower dose level, and so on. The MTD is the highest dose level in which ≤ 1 participant has a DLT. There will be no intra-participant dose escalation allowed.

Once the MTD has been determined, the MTD cohort will be opened for an estimated additional 6 participants. These participants will adhere to the identical protocol of the rest of their cohort.

Product will be administered IV every 7 days for 3 weeks.

For a detailed review of visits, please see Appendix 1.

Total duration of the study is expected to be about one year.

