10.2 Visit 1 – may also be Screening visit (Day 0)

1. Review the study with the participant/participant's legal representative and obtain written informed consent and HIPAA authorization and assent, if appropriate.
2. Assign the participant a unique screening number.
3. Record concomitant medications.
4. Perform abbreviated physical exam
5. Measure and record height and weight.
6. Obtain and record vital signs.
7. Initiate epilepsy diary

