10.4 Visits 3, 4, & 5: ABI-009 Doses 1-3 (+/-2 days)

1. Review adverse events.
2. Review epilepsy diary.
3. Investigator opinion regarding seizures recorded: same, worse, somewhat better, better.
4. Record changes to concomitant medications.
5. Perform abbreviated physical exam
6. Measure and record height and weight.
 - a. BSA calculation (Calculated ONLY on Dose 1 visit; to be recalculated only if the weight changes by > 10% in subsequent cycles)
7. Obtain and record vital signs. Pulse oximetry must be >93 to continue.
8. Collect blood for clinical laboratory tests (chemistry, hematology).
9. Laboratory assessments as required per the schedule of evaluations
 - a. Complete Blood Count (CBC) with differential and platelet count
 - b. Blood chemistry assessment (required for Visit 4), including:
 - i. Sodium, potassium, chloride, bicarbonate, calcium, fasting glucose, albumin,
 - ii. Total protein, BUN, serum creatinine.
 - iii. Total bilirubin, AST, ALT, alkaline phosphatase, uric acid, phosphorus,
 - iv. Fasting serum lipid profile (total cholesterol, triglycerides, HDL and LDL)
10. Coagulation assessment, including prothrombin time, partial thromboplastin time, international normalized ratio (PT/PTT/INR)
11. Whole blood rapamycin trough levels
12. Dose modification as appropriate (only in the case of toxicities mandating a dose change as per section 8.6)
13. Administer study drug

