APPENDIX 1. SCHEDULE OF EVENTS

	SCREENING DAY -14 TO DAY 0*	VISIT 1: DAY 0	VISIT 2: DAY 30**	VISIT 3: DOSE 1	VISITS 4&5: DOSES 2 AND 3	VISIT 6: ONE WEEK POST- DOSING	VISITS 7&8: 30 AND 60 DAYS POST-DOSING	VISIT 9: 90 DAYS POST- DOSING	EARLY PERMANENT DISCONTINUATION
Informed Consent Process	X								
Enrollment Eligibility Checklist	X								
Demographics	X								
Extended Physical Exam	X								
Neurological Exam	X								
Hepatitis C, and Hepatitis B, HIV if necessary ^A	X								
Epilepsy and Medical History	X								
Height, Weight, and BSA	X			X				X	X
Vitals	X		X	X	X	X			
Pulse Oximetry ^F	X		X	X	X				
CBC with Differential ^C	X		X	X	X	X	X ^B (visit 7 only)		X
Serum Chemistries with Coagulation Assessment ^E	X		X	X	X ^B (visit 4 required)	X ^B	X ^B (visit 7 only)		X
Urine Pregnancy ^G	X		X						
Study Continuation Checklist			X	X	X	X	X		
Abbreviated Physical Exam		X	X	X	X	X	X ^D		X
Concomitant Medication Review		X	X	X	X	X	X	X	X
Dispense Seizure Diary and Glossary		X							
Administer QOLCE, NCBRF, & C-SSRS			X			X		X	X
Review Seizure Diary			X	X	X	X	X		X
Investigator Opinion			X	X	X	X	X		
Dosing Checklist				X	X				
Study Drug Administration				X	X				
Adverse Events			X	X	X	X	X	X	X
Whole Blood Rapamycin Level ^H					X	X			X

*Screening may be combined with Visit 1

**Visit 2 may also be Visit 3 Dose 1

^A Hepatitis C (and if necessary, Hepatitis B) test: 2 mL SST gold top tube. HIV seropositivity test, if necessary: 2 mL gold top tube. If testing for all together, can use one 4 mL SST gold top tube.

^B Only if previous chemistries or coagulation profiles are abnormal or are otherwise clinically indicated.

^C CBC with differential: 1 mL EDTA lavender top tubes if testing with blood trough rapamycin levels. If testing alone can collect only 0.5 mL in EDTA tube.

^D Only at 30 days post-treatment

^E 2 x 4 mL SST gold top tubes. Serum chemistry: Na, K, Cl, CO₂, Ca, fasting glucose, BUN, creatinine, total protein, albumin, total bilirubin, aspartate aminotransferase (AST/SGOT), alanine aminotransferase (ALT/SGPT), alkaline phosphatase, uric acid, Ph, fasting serum lipid profile. Coagulation assessment: 1.8 mL Sodium Citrate light blue top tubes. Coagulation assessment including prothrombin time, partial thromboplastin time, international normalized ratio (PT/PTT/INR).

^F Must be greater than 93% on room air to continue with study procedures

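### The analysis baseline is fixed at Days 0-30, yet the first infusion is allowed from Day 28, so up to 3 of 31 baseline days can be on drug

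*Combined protocol and SAP*

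**What the plan says.** Section 15.1 states that for analysis the "baseline period will be defined as Days 0-30". It does not tie the end of that period to the first infusion. Other sections set the timing of the infusion:

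- The heading of 10.3 places Visit 2 at "End of Baseline (Day 30 +5/-2 days", that is, Day 28 to Day 35.
- A footnote to Appendix 1 reads "Visit 2 may also be Visit 3 Dose 1".
- The heading of 10.4 gives the dosing visits a window, "ABI-009 Doses 1-3 (+/-2 days", but no study day to which Visit 3 is anchored and no maximum gap after Visit 2.
- Section 4.1 describes "a 4-week baseline period to obtain baseline outcome rates" and has ABI-009 start once that period is over. Section 15.1.1 makes every analysis a before-and-after-treatment comparison within the participant.
- Section 15.5 divides the change in seizure rate by the baseline rate, sets the response threshold at a 25% reduction, and computes rates over days with known seizure information.
- Section 10.2 says "Initiate epilepsy diary" at Visit 1 (Day 0). Section 10.3 then instructs staff at Visit 2: "Ensure participant has had >8 seizures in the last 30 days without 2 weeks of seizure freedom to continue onto next phase".

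**The concern.** The run-in is the only pre-drug comparison in this single-arm study, and its seizure rate is the denominator of the percentage reduction and of the response rate. A window fixed by study day, combined with a first infusion that may come before the window closes, lets treated days count as baseline. If the drug works, those days lower the baseline rate and shrink the measured reduction. With at most 18 participants, moving one person across the 25% line shifts the response rate by at least 1/18, or 5.6 percentage points.

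In the other direction, a first infusion after Day 31 leaves drug-free diary days outside the baseline.

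**Working it through.** The plan has no calculated figure to reproduce here, because Days 0-30 is a definition. The check is day counting, followed by a dilution formula.

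**Inputs.** Baseline is Days 0 to 30 inclusive, or 31 days (15.1). Visit 2 falls on Day 28 to 35 (10.3). Dose 1 may be given at Visit 2 (Appendix 1). The study diary starts on Day 0 (10.2). The response threshold is 25% (15.5). Day 28 is the earliest possible Dose 1, because the Visit 2 checks must come first or on the same day.

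**Day counts, with Visit 2 and Dose 1 combined**

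| Dose 1 on | On-drug days in baseline (dose day counted / not counted) | Pre-drug days left out | The 30 days before the visit |
|---|---|---|---|
| Day 28 | 3 / 2 | 0 | Days -2 to 27 |
| Day 29 | 2 / 1 | 0 | Days -1 to 28 |
| Day 30 | 1 / 0 | 0 | Days 0 to 29 |
| Day 31 | 0 / 0 | 0 | Days 1 to 30 |
| Day 33 | 0 / 0 | 2 | Days 3 to 32 |
| Day 35 | 0 / 0 | 4 | Days 5 to 34 |

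The largest overlap is 3/31 = 9.7% of the baseline. At the nominal Day 30 it is the dose day alone.

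**Dilution.** Let r be the true fractional reduction and k the number of on-drug days in the baseline. Assume a constant underlying rate and a full effect from the first infusion onward. The measured baseline is then 1 - (k/31)r of the true baseline, and

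measured reduction = 1 - (1 - r) / (1 - (k/31)r).

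- k = 3, r = 0.25: 1 - 0.75/0.9758 = 23.1%. The baseline is understated by (3/31) × 0.25 = 2.4%.
- k = 3, r = 0.40: 1 - 0.60/0.9613 = 37.6%.
- k = 2, r = 0.25: 23.8%.
- k = 1, r = 0.25: 24.4%.

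The true reduction needed to measure exactly 25% is 0.25 / (1 - 0.75k/31). This gives 27.0% for k = 3, 26.3% for k = 2 and 25.6% for k = 1.

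**Late first infusion.** With Dose 1 on Day 35, Days 31 to 34 are left out: 4 of 35 pre-drug days, or 11.4%. For a Poisson count, the standard error of the baseline rate grows by √(35/31) = 1.06, about 6%. The expected baseline rate does not change.

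**After the fix.** Ending baseline on the day before Dose 1 gives 28, 30 or 35 days for Dose 1 on Day 28, 30 or 35. No on-drug days are included and no pre-drug days are lost.

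**The case against.** The best defence is that Day 0 and Day 30 are visit labels. Appendix 1 uses them that way, and 10.3 calls Visit 2 the end of baseline, so Days 0-30 could mean Visit 1 to Visit 2. Sections 4.1 and 15.1.1 point the same way. This shows what was intended, but 15.1 still states a day range with no first-dose cut-off, and an analyst who programs it literally would include the treated days. Section 15.1 also promises a detailed SAP that may modify the plan. That SAP is not in the document, and the present wording is what it would inherit.

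Several limits on size stand in full. The 23.1% figure needs the earliest Visit 2, combined visits, the dose day counted as treated, and an instant effect. The documents do not support instant onset: in the animal work in section 1.6, three days of rapamycin pre-treatment left acute seizure severity unchanged. A participant near the entry floor, with 9 seizures, carries a Poisson error of about 1/√9 = 33% on the baseline count, far above a 2.4% shift.

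A reader might also draw stronger conclusions that the documents do not bear out:

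- That the late case biases the result. It only discards some drug-free days.
- That the Visit 2 seizure count must cover the same days as the analysis baseline. It is an eligibility check, and no analysis requires the two windows to match.
- That the 4 weeks in 4.1 contradict the 31 days in 15.1. This is ordinary rounding of a one-month run-in.
- That the study diary must be the only source for the count. Section 6.2 requires the same count for enrollment from a daily diary, which implies that records from before Visit 1 may exist.

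**Conclusion.** The definition in 15.1 conflicts with the visit rules and with the plan's own pre-treatment intent, and it should be corrected. Its effect is modest. At most 3 of 31 baseline days are affected, and only for participants dosed on Days 28 to 30. The documents do not show how many that would be. Under the upper-bound assumptions, only true reductions between 25% and about 27% change response status. A beneficial effect is understated, so the error cannot create a false signal of benefit.

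Only secondary efficacy endpoints are touched. Dose-limiting toxicity and the maximum tolerated dose do not use this window, and section 15.3 defines treatment-emergent events by the start of treatment. It would be wrong to infer that the trial's main conclusions are at risk.

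One smaller inconsistency remains. At a Day 28 Visit 2, the 30 days before the visit begin two days before the study diary does (one day at a Day 29 visit), and the protocol does not say which record covers them.

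**What to change.** In 15.1, define baseline as Day 0 through the day before the first ABI-009 infusion, with the seizure rate taken over the known diary days in that interval. Carry the same definition into the SAP before any data are analysed, since choosing the window afterwards in an open-label study would be a post-hoc decision. The cost is one sentence and no new data: the diary is daily, and 15.5 already divides by known days, so a baseline of varying length needs no further rule.

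Separately, reconcile 6.2, 10.2 and 10.3 on which seizure records support the 30-day count when Visit 2 falls before Day 30. How to resolve that is for the sponsor; no change to the dosing day or to the rule for continuing is proposed here.
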